#### **3.3 Centers Pools**

This is a single centre study, therefore pooling of centers is not required.

#### **3.4 Timepoints and Visit Windows**

The study schedule should be followed as per protocol. Deviations from the study schedule with respect to visit timings will be reviewed on a case-by-case basis to determine whether the data should be excluded from the Per-Protocol (PP) analysis ([Section 4.1.2](#)).

### **4 Data Analysis**

Data analysis will be performed by inVentiv Health Clinical. The statistical analysis software used will be SAS version 9.4 (Studio).

Prior to database closure a Blinded Data Review Meeting (BDRM) will be conducted in which various aspects of the trial will be discussed and agreed.

Unless otherwise described below, all listings will be produced for all randomized subjects.

## 4.1 Populations for Analysis

### 4.1.1 Subject Disposition

Screen failures are defined as subjects who consent to participate in the clinical study but are not subsequently randomized. A summary will be provided of the number of subjects screened and the number of screen failures with reasons why subjects are not randomized (Table 14.1.1). Percentages for not randomized subjects will be based on number of screened subjects.

Subject disposition will be summarized as the number and percentage of subjects who complete the study, with the number who discontinue broken down by reason for discontinuation (Table 14.1.1). The percentages are based on the total number of subjects randomized. The table will also summarise the number and percent of subjects assigned to each analysis population (defined in Section 4.1.3). The summary will be presented by treatment and overall.

Subject disposition including the subject status (completer, Yes/No), critical demographic data (age, sex, race and ethnicity), the duration of treatment (defined as date of completion or withdrawal minus date of first product application) and the specific reason for discontinuation, will be listed by treatment group for randomized subjects (Listing 16.2.1.1) and non-randomized subjects (Listing 16.2.1.2) separately.

### 4.1.2 Protocol Deviations

Important major protocol deviations (including deviations related to study inclusion/exclusion criteria, conduct of the trial, patient management or patient assessment) will be summarized and listed. Details of possible protocol deviation are provided in Protocol Deviation Management Plan (PDMP).

Protocol deviations will be tracked by the study team throughout the conduct of the study. Data will be reviewed prior to unblinding and closure of the database to ensure all important deviations are captured and categorized.

Major deviations of the protocol procedures identified as liable to influence the efficacy outcome may include, but will not be necessarily limited to, the following:

- Violations of inclusion or exclusion criteria that are deemed to affect efficacy
- Medical history which is deemed to affect efficacy.
- Use of prohibited treatment or medication before or during the study, which is felt to affect the assessment of efficacy.
- Not receiving randomised treatment.
- Treatment non-compliance.
- Assessments outside the scheduled time windows.
- Visit outside the planned schedule.
- Protocol deviations.

- Any other reason identified likely to affect efficacy.

Further deviations liable to influence the efficacy outcome will be given in the Review Listing Requirement (RLR) document where major deviations will be identified at the BDRM. The number and percentage of subjects with any major protocol deviation and with each type of major protocol deviations will be presented by treatment (Table 14.1.2) and listed (Listing 16.2.2.1). Any minor protocol deviations will be listed similarly (Listing 16.2.2.2).

#### 4.1.3 Analysis Populations

Five analysis populations are defined.

Population	Definition / Criteria	Analyses Evaluated
All Screened Subjects	
 
• All subjects who enter the study and sign the informed consent form. This population includes screen failures as well as those that are randomized.
 
	
 
• Disposition, AE listing
 

Randomized	
 
• All subjects who are randomized and may or may not receive dose of the investigational product.
 
• Any subject who receives a treatment randomization number will be considered to have been randomized.
 
	
 
• Protocol violations, AE, efficacy, demographic characteristic, disposition and medical history listings
 

Safety	
 
• Comprise of all randomized subjects who receive at least one dose of study treatment.
 
• This population will be based on the treatment the subject actually received.
 
	
 
• Safety
 

Intent-To-Treat (ITT)	
 
• Comprise of all randomized subjects who receive at least one dose of study treatment and have at least one post-baseline efficacy evaluation.
 
• This population will be based on the treatment to which the subject was randomized.
 
	
 
• Efficacy
 

Per-Protocol	
 
• All subjects who are assessed as sufficiently compliant with study procedures and restrictions.
 
• Subjects with major protocol deviations will be excluded. Depending on the nature of the major protocol deviation and impact on the efficacy variable (s),
 
	
 
• Efficacy
 

Population	Definition / Criteria	Analyses Evaluated
	subjects will be either completely excluded from PP population or only partially excluded from the PP analyses. This will be determined on a case-by-case basis.	

The primary population for assessment of efficacy will be the ITT Population. A PP analysis will be performed on the primary and secondary efficacy variable if more than 10% of the subjects in the ITT Population are excluded from the PP Population.

Subjects excluded from the analysis populations will be listed ([Listing 16.2.3.1](#)).

## 4.2 Subject Demographics and Other Baseline Characteristics

### 4.2.1 Demographic Characteristics

Descriptive statistics (number of subjects, mean, standard deviation, median, minimum and maximum for continuous variables, and frequency and percentage for categorical variables) will be presented for demographic data by treatment group and overall. These data include age, gender, race, ethnicity and Schiff stratification categories and will be presented for the Safety ([Table 14.1.4.1](#)), ITT ([Table 14.1.4.2](#)) and if required on the PP Population ([Table 14.1.4.3](#)).

Demographic information will be listed ([Listing 16.2.4.1](#)) for all randomized subjects.

### 4.2.2 General Medical History

Medical history data will be listed ([Listing 16.2.4.2](#)) with start date and end date or ongoing at the start of study drug. A data listing will also be produced for evaluation of protocol violations at the blinded data review stage.

## 4.3 Study Product Compliance and Use of Other Therapy

### 4.3.1 Study Product Compliance and Exposure

Brushing compliance (using study product twice daily) will be presented in the listing ([Listing 16.2.5.3](#)) This listing also produced for the blinded data review .

Supervised brushing (subject number, date of visit and time of the supervised procedure and reason why the supervised brushing was not performed according to the protocol) will be listed in the listing ([Listing 16.2.5.4](#)). This listings also produced for the blinded data review.

Exposure to the study product will be listed in the listing ([Listing 16.1.7](#))

### 4.3.2 Prior and Concomitant Medication

Prior treatment will be listed by subject, with, indication, dose, dose form, frequency, route, start date and end date ([Listing 16.2.5.1](#)). Prior treatment are defined as those which stopped before the first application of the study product. Concomitant treatment will be listed similarly ([Listing 16.2.5.2](#)). Concomitant treatment are defined as those ongoing or started on or after the first application of the study product.

#### **4.3.3 Other Therapy/Rescue Medication**

Not Applicable.

### **4.4 Analysis of Efficacy**

#### **4.4.1 Primary Efficacy Endpoint**

##### **4.4.1.1 Primary Efficacy Endpoint Definition**

The change from baseline in Schiff sensitivity score at Week 8 is the primary efficacy endpoint.

The subjects Schiff sensitivity score will be derived as the average score of the 2 test teeth at each visit assessed. The change from baseline will be derived from the individual teeth first before calculating the average change of the 2 test teeth. For post-baseline observations, the average will be calculated only across teeth that have both a valid baseline and a valid post-baseline assessment.

Summary statistics of the observed mean Schiff sensitivity scores and changes from baseline will be presented by treatment at Baseline, Week 4 and Week 8 on the ITT Population ([Table 14.2.1.1](#)).

##### **4.4.1.2 Statistical Hypothesis, Model, and Method of Analysis**

The primary analysis is a comparison of the mean change from baseline Schiff sensitivity score between Test Product and Negative Control at Week 8.

The null hypothesis for the primary endpoint is that the mean change from baseline in Schiff sensitivity score is equal between the 2 products.

$$H_0: \mu_1 = \mu_2$$

The alternative hypothesis is that the mean change from baseline in Schiff sensitivity score is not equal between the 2 products.

$$H_1: \mu_1 \neq \mu_2$$

The change from baseline in Schiff sensitivity score at Week 8 will be analyzed using Analysis of Covariance (ANCOVA) with treatment as factor and mean baseline Schiff sensitivity score as covariate. Note that since the baseline Schiff sensitivity score will be included as a covariate, the baseline Schiff stratification value will not be included in the

---

model. Adjusted means of all treatments and their standard error (SE), P-value and 95% confidence interval (CIs) will be presented on the ITT Population (Table 14.2.1.2). Treatment differences of the treatment comparisons and SE of it will also be provided together with P-values and 95% CIs.

The assumption of normality and homogeneity of variance in the ANCOVA model will be investigated and if violated, data transformations will be investigated. If suitable transformations cannot be found, non-parametric Van Elteren tests will be performed adjusting for the maximum baseline Schiff sensitivity scores and results will be compared with the ANCOVA results. If the inferences from the 2 analyses are similar then both sets of results will be reported and emphasis will be made on the ANCOVA results. In case of discrepancies between p-values of ANCOVA and Van Elteren analysis, inferences will be drawn on the non-parametric analysis.

To visually inspect the treatment effect on Schiff sensitivity scores, a plot across time (Baseline, Week 4 and Week 8) will be displayed with raw means and SE bars. The plot will display a different symbol line for each treatment group (Figure 14.2.1).

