# 10 STATISTICAL CONSIDERATIONS AND DATA ANALYSES

## 10.1 Sample Size Determination

Change from baseline in Schiff sensitivity score will be used to evaluate treatment effects with regard to the primary objective. With 55 evaluable subjects per group, the study will have 80% power to detect a mean difference of 0.33 (SD=0.619) in change from baseline in Schiff sensitivity score after 8 weeks of treatment.

The estimate of SD was obtained from GSKCH study 205794. The sample size is based on carrying out two-tailed two sample t-test at a 5% significance level.

Therefore, to allow for dropouts a sufficient amount of subjects will be screened to randomize approximately 180 subjects to ensure 165 subjects (approximately 55 per arm) complete the study.

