## **10.2** Statistical Methods and Analytical Plan

Additional details of the proposed statistical analysis will be documented in the statistical analysis plan (SAP), which will be written following finalization of the protocol and prior to study unblinding.

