#### 10.2.2 Primary Analysis

The primary efficacy variable is the change from baseline in Schiff sensitivity score at 8 weeks. The primary comparison is between the Experimental formulation and the negative control. As there is only a single primary objective no adjustment for multiple comparisons is required.

The Schiff sensitivity score is derived as the average score of the two test teeth. The change from baseline is derived from the individual teeth first before calculating the average change of the two test teeth.

GlaxoSmithKline Consumer Healthcare Confidential Template Version Effective: 22-Jun-2017 Page **47** of **60** 

The change from baseline in Schiff sensitivity score will be analysed using analysis of covariance (ANCOVA) with treatment as factor and baseline Schiff sensitivity score as a covariate. Note that since the baseline Schiff sensitivity score will be included as a covariate, the baseline Schiff stratification value will not be included in the model.

The assumption of normality and homogeneity of variance in the ANCOVA model will be investigated. In case of violation of these assumptions a suitable transformation or a nonparametric method eg the van Elteren test, adjusting for the maximum baseline Schiff Sensitivity scores will be performed and results will be compared with the ANCOVA results. If the inferences from the two analyses are similar, then both sets of results will be reported and emphasis will be made on the ANCOVA results. If there are differences between the inferences, then the emphasis will be on the non-parametric analysis.

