
Protocol 208153

Program Run Date:xxxx

Table 14.2.1.1  
Summary Statistics of Evaporative (Air) Schiff Sensitivity Score  
Intent-to-Treat Population

Study Population: Intent to Treat (N=XXX)

Visit		Test Product (N=XX)		Negative Control (N=XX)		Positive Control (N=XX)		Overall
		Observed Value	Change from Baseline	Observed Value	Change from Baseline	Observed Value	Change from Baseline	Observed Value
BASELINE	n	XX		XX		XX		XX
	n (Missing)	XX		XX		XX		XX
	MEAN	X.XX		X.XX		X.XX		X.XX
	SE	X.XX		X.XX		X.XX		X.XXX
	SD	X.XXX		X.XXX		X.XXX		X.XXX
	MEDIAN	X.X		X.X		X.X		X.XX
	MINIMUM	X.X		X.X		X.X		X.XX
	MAXIMUM	X.X		X.X		X.X		X.X
WEEK 4	n	XX	XX	XX	XX	XX	XX	
	n (Missing)	XX		XX		XX		XX
	MEAN	X.XX	X.XX	X.XX	X.XX	X.XX	X.XX	
	SE	X.XX	X.XX	X.XX	X.XX	X.XX	X.XX	
	SD	X.XXX	X.XXX	X.XXX	X.XXX	X.XXX	X.XXX	
	MEDIAN	X.X	X.X	X.X	X.X	X.X	X.X	
	MINIMUM	X.X	X.X	X.X	X.X	X.X	X.X	
	MAXIMUM	X.X	X.X	X.X	X.X	X.X	X.X	

Stannous Fluoride (SnF2)

208153

Final Statistical Reporting and Analysis plan V1.0 14 Dec 2017

---

Visit	Test Product (N=XX)		Negative Control (N=XX)		Positive Control (N=XX)		Overall
	Observed Value	Change from Baseline	Observed Value	Change from Baseline	Observed Value	Change from Baseline	Observed Value
WEEK 8	SAME AS WEEK 4.						

---

Stannous Fluoride (SnF2)

208153

Final Statistical Reporting and Analysis plan V1.0 14 Dec 2017

Protocol 208153

Program Run Date:xxxx

Table 14.2.1.2  
Statistical Analysis of Change from Baseline in Evaporative (Air) Schiff Sensitivity Score  
Intent-to-Treat Population

Study Population: Intent to Treat (N=XXX)

	Test Product (N=XX)	Negative Control (N=XX)	Positive Control (N=XX)		
WEEK 4					
ADJUSTED MEAN [1]	XX.XX	XX.XX	XX.XX		
SE [1]	XX.XXX	XX.XXX	XX.XXX		
95% CI [1]	(XX.XXX, XX.XXX)	(XX.XXX, XX.XXX)	(XX.XXX, XX.XXX)		
P-VALUE [1]	0.XXXX	0.XXXX	0.XXXX		
COMPARISONS BETWEEN TREATMENTS	DIFFERENCE (SE) [1]	95% CI [1]	P-VALUE [1]	MEAN DIFFERENCE % [2]	.
TEST PRODUCT VERSUS NEGATIVE CONTROL [1] *	XX.XX (XX.XXX)	(XX.XXX, XX.XXX)	0.XXX	xx.xx	
TEST PRODUCT VERSUS POSITIVE CONTROL [1]	XX.XX (XX.XXX)	(XX.XXX, XX.XXX)	0.XXX	XX.XX	
NEGATIVE CONTROL VERSUS POSITIVE CONTROL [1]	XX.XX (XX.XXX)	(XX.XXX, XX.XXX)	0.XXX		
WEEK 8 (AS ABOVE FOR WEEK 4)					
...					

\* Test Product versus Negative Control at Week 8 is a primary endpoint comparison.

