[1] From ANCOVA model with treatment as factor and baseline Schiff score as covariate. Difference is first named treatment minus second named treatment such that a negative difference favors the first named treatment.

[2] For the Chinese Ministry of Health guideline requirement to demonstrate difference between Test Product and Control (Positive or Negative) in the observed raw means. It is Calculated as  $100 * (\text{Test Product} - \text{Control}) / \text{Control}$ .

Page x of y

PPD

GlaxoSmithKline Consumer Healthcare Confidential

Stannous Fluoride (SnF2)

208153

Final Statistical Reporting and Analysis plan V1.0 14 Dec 2017

*Programming Note: For Table 14.2.2.2 and 14.2.2.4: please update footnote [1] as  
[1] From ANCOVA model with treatment and baseline Schiff stratification as factors and baseline tactile threshold as a covariate. Difference is the first named  
treatment minus second named treatment such that a positive difference favors the first named treatment.*

Stannous Fluoride (SnF2)

208153

Final Statistical Reporting and Analysis plan V1.0 14 Dec 2017

Protocol 208153

Program Run Date:xxxx

Table 14.3.1.1  
Treatment Emergent Adverse Event by SOC and Preferred Term  
Safety Population

Study Population: Safety Population (N=xx)

SOC Preferred Term	Test Product (N=XX)		Negative Control (N=XX)		Positive Control (N=XX)		Overall (N=XX)	
	n (%)	nAE	n (%)	nAE	n (%)	nAE	n (%)	nAE
NUMBER OF SUBJECTS WITH AT LEAST ONE AE	xx (xx.x)	xx	xx (xx.x)	xx	xx (xx.x)	xx	xx (xx.x)	xx
NUMBER OF SUBJECTS WITH NO AE	xx (xx.x)	xx	xx (xx.x)	xx	xx (xx.x)	xx	xx (xx.x)	xx
SKIN AND SUBCUTANEOUS TISSUE DISORDERS	xx (xx.x)	xx	xx (xx.x)	xx	xx (xx.x)	xx	xx (xx.x)	xx
ERYTHEMA	xx (xx.x)	xx	xx (xx.x)	xx	xx (xx.x)	xx	xx (xx.x)	xx
DERMATITIS	xx (xx.x)	xx	xx (xx.x)	xx	xx (xx.x)	xx	xx (xx.x)	xx
GASTROINTESTINAL SYSTEM	xx (xx.x)	xx	xx (xx.x)	xx	xx (xx.x)	xx	xx (xx.x)	xx
ABDOMINAL PAIN	xx (xx.x)	xx	xx (xx.x)	xx	xx (xx.x)	xx	xx (xx.x)	xx
DRY MOUTH	xx (xx.x)	xx	xx (xx.x)	xx	xx (xx.x)	xx	xx (xx.x)	xx
VOMITTING	xx (xx.x)	xx	xx (xx.x)	xx	xx (xx.x)	xx	xx (xx.x)	xx

Etc.

n (%) = Number (percent) of subjects nAE = Number of adverse events.

Page x of y

PPD

Stannous Fluoride (SnF2)

208153

Final Statistical Reporting and Analysis plan V1.0 14 Dec 2017

Protocol 208153

Program Run Date:xxxx

Listing 16.1.7  
Randomization Information  
Randomized Population

Study Population: Randomized (N=xx)  
Stratum 1: Maximum Schiff score =2

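### Does leaving *violated* and *suitable* undefined in the SAP's ANCOVA assumption check leave the primary test open?

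*SAP*

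**What the plan says.** The primary analysis is an ANCOVA of the Week 8 change in Schiff score, with treatment as factor and mean baseline score as covariate. SAP 4.4.1.2 then sets out a sequence:

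- **Check:** "The assumption of normality and homogeneity of variance in the ANCOVA model will be investigated and if violated, data transformations will be investigated".
- **Fallback:** "If suitable transformations cannot be found, non-parametric Van Elteren tests will be performed", stratified by maximum baseline Schiff score and compared with the ANCOVA.
- **Tie-break:** if the two agree, emphasis stays on the ANCOVA. If they do not: "In case of discrepancies between p-values of ANCOVA and Van Elteren analysis, inferences will be drawn on the non-parametric analysis".

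SAP 4.5.1 repeats this for the tactile threshold, and SAP 4.6 carries it to the exploratory comparisons. The shell for Table 14.2.1.2 takes all three comparisons "From ANCOVA model with treatment as factor and baseline Schiff score as covariate", so one three-arm model supplies the primary contrast.

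Protocol 10.2.2 offers "a suitable transformation or a nonparametric method eg the van Elteren test" without ordering the two. Protocol 10.2 leaves further statistical detail to the SAP.

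**The concern.** Three things are unstated: what counts as a violation, which transformations may be tried and when one is acceptable, and what role an accepted transformed ANCOVA has. In that last branch van Elteren is not called for, and the tie-break covers only ANCOVA against van Elteren.

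The check is likely to matter. Each test tooth starts at Schiff 2 or 3 and is scored 0 to 3 afterwards, so the two-tooth mean change runs from -3 to +1 in half-unit steps. That is (1 + 3)/0.5 + 1 = 9 possible values, which cannot be exactly normal.

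Study success (Protocol section 2) requires a significant primary result. SAP 2.2 places the final analyses after the randomization codes are released, and no blinded assumption check is assigned to the Blinded Data Review Meeting. At stake would be an inflated type I error, or a primary conclusion that depends on the analyst's judgement.

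**Working it through.** **1. The plan's own figure.** Inputs from Protocol 10.1 and SAP 1.4: 55 per arm, difference 0.33, SD 0.619, two-sided 5%.

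SE = 0.619 × √(2/55) = 0.1180. Then 0.33/0.1180 - 1.96 = 0.836, and Φ(0.836) = 79.8%. The exact t calculation gives 79.1%. The stated 80% is reproduced.

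**2. Does the unstated cut-off change the error rate?** Simulation of three arms of 55, with two teeth scored 0-3 and SD of change about 0.64. *Violated* is taken to mean Shapiro-Wilk or Levene on the residuals below a cut-off. Van Elteren then decides, and no transformations are tried. There were 8,000 null trials and 4,000 at a difference of 0.34 (Monte Carlo SE about 0.25 and 0.6 points).

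| Rule | Triggered, null | Triggered, 0.34 | Type I error | Power |
|---|---|---|---|---|
| Cut-off 0.05 | 44% | 32% | 5.3% | 82.5% |
| Cut-off 0.01 | 14% | 8% | 5.3% | 82.8% |
| Cut-off 0.001 | 2% | 1% | 5.3% | 82.9% |
| ANCOVA alone | – | – | 5.3% | 82.9% |
| Van Elteren alone | – | – | 5.3% | 80.8% |

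The cut-off strongly affects which route is taken and hardly affects the error rate.

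An outer bound without transformations is an analyst who claims significance on either test. Type I error is then P(ANCOVA) + P(van Elteren) - P(both) = 5.26 + 5.28 - 3.98 = 6.56%, about 1.3 points above either test alone. Reaching it would mean choosing the trigger after seeing the p-values, because the tie-break gives any disagreement to van Elteren once that test has been run.

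**3. How often would two analysts disagree?** Simulation with SD about 0.62, positive-control SD 0.62 or about 0.53, 4,000 trials per scenario, no transformations.

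| Comparison | Null | Difference 0.34 |
|---|---|---|
| Cut-off 0.05 against 0.01 | 0.7% | 1.5-1.8% |
| Cut-off 0.05 against never triggering | 1.1-1.4% | 2.2-2.9% |
| ANCOVA against van Elteren in every trial | 2.1-2.3% | 4.8-4.9% |

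The last row overstates the practical problem, because two analysts diverge only in trials where one triggers and the other does not.

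**4. Does the transformation branch matter?** Wider simulation: 24 scenarios of 10,000 trials, covering six SD patterns, 15% or 40% of teeth at baseline 3, and difference 0 or 0.33. Triggers were at 5%. Square root and log of (change + 4), and its square, were tried in order. The sequence was run without transformations, with the accepted one deciding, and with the untransformed ANCOVA deciding.

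- Type I error of the sequence: 4.3-5.5%.
- A transformation was accepted in 1.4-8.0% of trials and changed the ANCOVA conclusion in at most 0.4%.

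Re-expressing a nine-valued score seldom makes it look normal, so the undefined branch is seldom entered.

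**5. Would a single named test do better?** Same 24 scenarios.

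| Deciding analysis | Type I error | Power, equal SDs | Power change against the sequence, all SD patterns |
|---|---|---|---|
| SAP sequence | 4.3-5.5% | 77.0-77.4% | – |
| Three-arm ANCOVA, HC3 standard error | 4.5-5.1% | 77.3% | -1.9 to +3.9 points |
| ANCOVA, test and negative arms only | 4.6-5.3% | 77.8% | -1.5 to +4.2 points |
| Van Elteren | 4.7-5.6% | 76.3-76.7% | -1.1 to +0.7 points |

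Every range of power change straddles zero. ANCOVA power is lower here than in step 2 (78.2% against 82.9% with equal SDs) because the assumed score distributions differ.

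**The case for a change.** The strongest case for acting is that the primary test should be unambiguous and that a few sentences would make it so. The text does omit all three items, and that part stands.

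A second argument concerns the three-arm model. Its residual variance includes the positive control, which plays no part in the primary contrast. With 165 - 4 = 161 degrees of freedom (critical t 1.975), the approximate type I error is 2 × P(Z > 1.975 × pooled SD / SD of the compared arms):

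- Positive control 0.50 against 0.62: pooled SD = √((2 × 0.62² + 0.50²)/3) = 0.583; 1.975 × 0.583/0.62 = 1.86; 6.3%.
- 0.50 against 0.70: pooled SD 0.640; 1.81; 7.1%.
- 0.75 against 0.62: pooled SD 0.666; 2.12; 3.4%.

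The arithmetic is right, but it describes a pooled ANCOVA that decides with no variance check. SAP 4.4.1.2 plans that check and a switch of test. The unequal SDs are also assumed; the documents give only 0.619. So this is a reason not to drop the homogeneity check, and it does not show a fault in the plan.

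The difference in ordering between Protocol 10.2.2 and the SAP is a permitted refinement. It is absent from SAP section 5, which is a clerical matter. Protocol 10.2.2 also helps with the open branch: it compares whichever alternative is used with the ANCOVA, and favours the non-parametric result when inferences differ.

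**Conclusion.** No change follows. The SAP leaves diagnostic detail to the analyst but fixes the endpoint, contrast, model, fallback, stratifier, order and tie-break. Under any of the cut-offs tried, applied mechanically, type I error stays near 5% (4.3-5.5% across the scenarios) and power stays close to that of every alternative. Different reasonable cut-offs change the conclusion in roughly 1-3% of trials, and the undefined transformation branch in at most 0.4%. Replacing the adaptive rule with a robust standard error, a two-arm fit or van Elteren alone is a matter of preference with no consistent gain. It would also depart from Protocol 10.2.2.

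These sizes rest on assumed tooth-score distributions, arm SDs, triggers and transformations. They apply to Schiff only: the tactile endpoint was not simulated, because the documents give no tactile SD or effect. They also assume the trigger is not chosen on the p-values; the bound of about 6.6% shows what that would cost without transformations.
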